7.1.2 Pre-screening

Prospective participants may be interviewed by telephone to determine whether they might be suitable candidates to participate in the trial. At the start of the telephone interview, interviewees will provide verbal consent confirming that they are willing to share personally identifiable information and their personal health information to determine if they are likely to qualify for participation in the trial.

The pre-screening interview will include questions about the participant's medical and psychiatric history, current treatment, etc. The interviewees will be asked to provide responses to the 17-question Life Events Checklist for DSM-5 (LEC-5) and the 20-question PTSD Checklist for DSM-5 (PCL-5). Qualified study site staff will provide individuals that pass the pre-screening assessment with IRB-approved study information and consent materials for review and consideration.

- If the prospective participant is not eligible or not interested in taking part in the trial their personal information will be destroyed at, apart from the summary reason for ineligibility, which will be retained on the Screening Log. An eCRF will not be completed for candidates who are not enrolled.

Pre-screening information will be retained for candidates who provide specific permission via verbal consent for utilization and retention of this information and who and provide written informed consent to participate in the trial. The Screening Log will be completed to include the qualified participant's screening number. The Screening Log will be maintained and kept up-to-date and be available for review by the study site monitor.

Table 1

Schedule of Events

Activity	Pre-Screen	Screening Period		Day 1	Day 2	Day 4 (Virtual)	Day 8 (±1 day)	EoT Day 30 1 Month (±5 days)	LTFU 3 Month (±7 days)
		-30 - to -1 (Can be extended)							
			Prior to Study Day 1						
Pre-Screen Verbal Consent ¹	X								
LEC-5 [^]		X							
PCL-5 [^]		X							
Informed Consent		X							
Medical History	X	X		X	X	X	X	X	X
Concomitant Medications	X	X		X					
Eligibility Criteria	X	X		X					
Height / Weight ²		X					X	◆ ¹⁴	
Physical Exam ³		X					X	◆ ¹⁴	
Vital Signs ⁴		X		X	X		X	X	X
Urine Pregnancy Test ⁵		X							
Urine Drug / Alcohol Tests		X		X				X	X
Clinical Laboratory Tests ⁶		X ⁶		X			X	X	
Electrocardiogram ⁷		X		X			X		
Dispense/Collect Wearable		X						◆ ¹⁴	X
Saliva – Epigenetic Test				X			X	◆ ¹⁴	
Pharmacokinetic Test ⁸				X					
Administer Study Drug				X					
One-to-One			X ¹⁵						
Group Session			X ¹⁵	X	X				
Ceremony				X					
GAD-7 ⁹		X		X	X	X	X	X	X
PHQ-9 ¹⁰		X		X	X	X	X	X	X
NIH-HEALS		X		X	X		X	X	X
BPI		X		X	X	X	X	X	X
C-SSRS ¹¹		X		X	X	X	X	X	X
POMS ¹²				X					
SDS		X						X	
WCS				X			X	X	
MEQ30-revised				X				X	
CEQ				X				X	
5D-ASC				X					
AUDIT ¹³		X						◆	X
DUDIT ¹³		X						◆	X
Adverse Events					X	X	X	X	X

CONFIDENTIAL

Footnotes:

1. Pre-Screen: Study site staff should obtain verbal consent to collect information to assess potential eligibility for the trial. If the individual does not qualify or chooses not to participate, the information collected will be deleted, save for more general, non-identifiable, information recorded on the Screening Log.
2. Height / Weight: Height and weight should be measured at Screening, but only weight will be measured at the Study Day 8 and EoT visits, respectively.
3. Physical Examination: The physical exam should be targeted to head, eyes, ears, nose, throat (HEENT), abdomen and extremities. A brief neurological exam also should be performed on cranial nerves 2 through 12 as well as assessments of motor reflexes and cerebellar function.
4. Vital Signs: Measure body temperature, pulse oximetry (SpO₂), heart rate, respiratory rate, and blood pressure
5. Urine Pregnancy: A urine sample should be collected for all females of childbearing potential. If needed, a serum-HCG test can be done to confirm an initial positive result.
6. Clinical Laboratory Tests: Blood samples will be collected to perform clinical laboratory evaluations. A urine sample, for urinalysis, only will be collected at Screening.
7. Electrocardiogram: A 12-lead ECG should be obtained. If there is a finding of QT interval prolongation (i.e., > 450 msec), then triplicate ECG recordings should be done within 5 (to 6) minutes for confirmation. If confirmed, the participant is not eligible to participate in the trial.
8. Pharmacokinetic: Blood samples for PK testing should be obtained at the following timepoints on Study Day 1: up to 30 minutes prior to study drug administration and then at the following timepoints after dosing — 30 minutes (±2 mins), 60 minutes (±5 mins), 90 minutes (±5 mins), 120 minutes (±5 mins), 4 hours (±15 mins) and 8 hours (±15 mins)
 - ^ To qualify for treatment, participants must self-report at least one traumatic event via the LEC-5 that the clinician considers causative for a diagnosis of PTSD; in addition, they must score at least 33 on the PCL-5
9. GAD-7: If a participant's score is ≥15 at Screening or on Study Day 1 (prior to study drug administration), the participant is not eligible for treatment.
10. PHQ-9: If a participant's score is ≥20 at Screening or on Study Day 1 (prior to study drug administration), the participant is not eligible for treatment.
11. C-SSRS: If at Screening or on Study Day 1 a participant's 'suicidal' assessment is scored as Category 4 (i.e., Active Suicidal Ideation with Some Intent to Act, without Specific Plan) or Category 5 (Active Suicidal Ideation with Specific Plan and Intent), the participant is not eligible to continue to participate in the trial and should be referred for appropriate psychiatric care.
12. POMS: On Study Day 1, after all protocol-mandated activities are complete, the clinician will assess the result of the POMS. If the posttreatment POMS score is not ≤125% of the baseline, pre-dose, value, the patient should be held overnight for observation. [Otherwise, if the score is ≤125% of the baseline, and if there are no other problems, the patient may be discharged to home (accompanied by a trusted adult).
13. AUDIT / DUDIT: The AUDIT and DUDIT should be completed at the Study Day 30 / End-of-Treatment visit if a participant prematurely discontinues from the trial (for any reason) and will not undergo the 3-month, Long-Term Follow-up visit.
14. ◆: The diamond reflects tests, examinations, assessments or other procedures that are to be completed the EoT visit if a participant is prematurely discontinued from further involvement in the trial and the particular protocol-mandated activity was not performed at the Study Day 8 visit.
15. **The One-to-One session as well as the Group session require participants to return to the study site on separate days. [Thus, the Screening Period can require three (3) visits to the study site.]**

Table 2
Study Day 1 Schedule of Events

Activity	Pre-Dose	Dose		Post Dose							
		Time 0	30 mins	60 mins	90 mins	120 mins	150 mins	180 mins	240 mins 4 hours	4.5, 5.0, 5.5, 6.0, 6.5, 7.0 and 7.5 hours	480 mins 8 hours
Medical History	X										
Concomitant Medications	X										
Eligibility Criteria	X										
Height / Weight ²	X										
Vital Signs ⁴	X	X	X	X	X	X	X	X	X	X*	X
Urine Pregnancy Test ⁵	X										
Urine Drug / Alcohol Tests	X										
Clinical Laboratory Tests ⁶	X										
Electrocardiogram ⁷	X										
Saliva – Epigenetic Test	X										
Pharmacokinetic Test ⁸	X	X	X	X	X	X	X	X	X		X
Administer Study Drug		X									
Ceremony	X										
GAD-7 ⁹	X										X
PHQ-9 ¹⁰	X										X
NIH-HEALS	X										
BPI											X
C-SSRS ¹¹	X										X
POMS ¹²	X										X
WCS											X
MEQ30-revised											X
CEQ											X
5D-ASC											X
Adverse Events	X	X	X	X	X	X	X	X	X	X	X

*Vital signs measured every 30 minutes, (i.e., 2 times per hour) during hours 4, 5, 6 and 7.

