Study Day 4: Approximately 72 hours after the time of study drug administration on Study Day 1, participants will undergo an individual, virtual (via web meeting, phone, etc.) integration session, and be assessed for adverse events including mental health issues as well as for changes in concomitant medications and clinician rating scales and patient QoL/PRO instruments will be completed.

Study Day 8: One week following Study Day 1, participants will return to the study site to undergo a physical exam, have vital signs measured, and share any changes in concomitant medications as well to be assessed for adverse events. Participants also will be administered clinical rating scales and complete their QoL and PRO instruments. Participants will provide blood and saliva samples for clinical laboratory evaluations and for epigenetic testing.

Study Day 30: Unless discontinued from participation earlier, at one month following Study Day 1, participants will return to the study site for an End-of-Treatment (EOT) visit. Patients that prematurely discontinued participation on, or after being treated on Study Day 1 will be encouraged to return to the study site for the EoT visit as soon as possible and need not wait till Study Day 30).

At the EoT visit, participants will be assessed for adverse events and changes in concomitant medications, have vital signs measured, provide urine samples for drug and alcohol screening and blood samples for clinical laboratory evaluations as well as undergo clinical rating scale assessments and complete their QoL and PRO instruments.

Study Day 90: Three months following Study Day 1, participants will return to the research study center for the Long-Term Follow-up (LTFU) visit. At the LTFU visit, participants will be assessed for adverse events deemed to be 'possibly' or 'probably' related to the single dose of the investigational product administered on Study Day 1 and/or to assess any AEs that were not resolved by the EoT visit.

Participants also will have vital signs measured, provide urine samples for drug and alcohol testing as well as undergo and/or complete rating scale assessments and QoL and PRO

instruments, respectively.

Participants also will return the health tracking wearable device and the data collected will be downloaded to the trial database.

Upon completion of the 3-month LTFU visit and after the study site staff obtain all outstanding data, participants will have completed the study.

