4.4. Study Endpoints

4.4.1 Primary Endpoints

Primary endpoints will be assessed using descriptive statistics. The statistical approaches are described Section 13.3 and will be detailed in the Statistical Analysis Plan (SAP) that will be developed and finalized before any analyses are undertaken.

- Number/Incidence of adverse events (AEs), and serious adverse events (SAEs) graded using the National Cancer Institute (NCI) Common Terminology Criteria for Adverse Events (CTCAE) version 5.0.
 - Number/Incidence of AE's related to clinically significant ECG/cardiac abnormalities

- Number/Incidence of AE's related to Heart Rate
 - Tachycardia (HR>100 bpm)
 - Bradycardia (HR < 50 bpm)
- Number/Incidence of AE's related to Blood Pressure
 - Hypotension
 - Hypertension
- Number/Incidence of AE's related to Liver Function
 - Liver function tests
- Number/Incidence of AE's related to Kidney Function
 - Renal function tests
- Number/Incidence of Mental and Psychotic AE's

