- Participants will identify a trusted adult who will accompany them on their ride home and the same or another adult who will stay with them overnight at their residence after being discharged from the study site on Study Day 1.

7.1.4 Study Day 1

Study Day 1 will be scheduled after the participant completes all the required Screening Period activities and is deemed to remain eligible for treatment with the study drug. There are three portions of the Study Day 1 visit including: consist of (i) confirming eligibility and performing baseline measurements for multiple primary, secondary and exploratory endpoint assessments, prior to study drug administration, (iii) self-administration of study drug under supervision, and (iv) observing participants for 8-hours post-dose for adverse events including collection of blood samples for pharmacokinetic profiling, completing clinician rating scales, among other activities.

The following protocol mandated activities, tests, examinations, assessments and procedures will be performed on Study Day 1:

Pre-Dose and Baseline Assessments

- Inquire about any changes in the participant's health and review concomitant medications/therapies (including psychotherapy and healthcare utilization).
- Obtain vital sign measurements.
- Perform a 12-lead ECG.
- Obtain blood samples for:
 - Clinical laboratory evaluations.
 - PK profiling –30 minutes (± 2 mins).
- Obtain urine samples for:
 - Pregnancy test in women of childbearing potential.
 - Qualitative rapid urine drug screen.
 - Qualitative urine ethyl glucuronide (EtG) test to assess alcohol consumption.
- Obtain saliva sample for epigenetic analysis.
- Review all eligibility criteria.
- Issue a research participant identification card ("wallet card") that indicates they are a research participant and may test positive for drugs. The card includes the Investigator's contact information, the telephone number for a 24-hour hotline for participant support, and instructions on how/when to present the card.
- The following clinician rating scales and participant QoL and PRO instruments should be

CONFIDENTIAL

administered and/or completed by the participant, respectively:

- POMS
- BPI
- C-SSRS (category ratings of 4 or 5 will exclude the participant)
- GAD-7 (scores of ≥ 15 will exclude the participant)
- PHQ-9 (scores of ≥ 20 will exclude the participant)
- Obtain/confirm the name and telephone number of an emergency contact from the participant for use throughout the study.

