7.1.8 Study Day 30 / End-of-Treatment (EoT) Assessments

One month after Study Day 1, participants will return to the study center on Study Day 30.

Likewise, any participant that self-administered study drug on Study Day 1, but that prematurely discontinues participation in the trial, for any reason, should be encouraged to undergo an End-of-Treatment visit. If the participant was discontinued prior to the Study Day 8 visit, additional tests and examinations will be performed at the EoT visit. For discontinued participants, the Study Day 8 visit should be scheduled as soon as practical to ensure collection of needed safety, and preliminary efficacy data.

- As noted in Section 8.1.1, participants that are prematurely discontinued before Study Day 3, for any reason except due to an adverse event, may be replaced, at the discretion of the Investigator.

The protocol-mandated tests, examinations, assessments and procedures to be performed during the Study Day 30 / EoT visit are presented below:

- Inquire about any changes in the participant's health in a non-suggestive manner and review concomitant medications/therapies (including psychotherapy and healthcare utilization).

CONFIDENTIAL

- Perform a brief physical exam and obtain weight (only if Study Day 8 visit was not completed).
- Obtain vital sign measurements.
- Obtain blood samples for clinical laboratory evaluations.
- Obtain saliva sample for epigenetic analysis (only if Study Day 8 visit was not completed).
- Obtain urine samples for:
 - Qualitative rapid urine drug screen.
 - Qualitative urine ethyl glucuronide (EtG) test to assess alcohol consumption.
- Review participant's use of health tracking wearable device and collect the device and download the data to the trial database (if the participant prematurely discontinued participation in the trial and will not be undergoing the 3-month Long Term Follow-up visit).
- Administer and/or have the participant complete the following clinician rating scales and participant QoL and PRO instruments, respectively:
 - GAD-7
 - PHQ-9
 - BPI
 - NIH HEALS
 - C-SSRS
 - SDS
 - AUDIT (only if the participant was prematurely discontinued)
 - DUDIT (only if the participant was prematurely discontinued)

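### A participant who discontinues before Day 8 has no scheduled post-dose ECG, because the ECG is the one Day 8 procedure that Table 1 neither repeats nor makes up at End-of-Treatment

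*Protocol*

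**What the plan says.** Table 1 marks the "Electrocardiogram" row at Screening, Day 1 and Day 8, and nowhere else. Table 2 puts the Day 1 ECG in the pre-dose column only. Section 7.1.4 agrees: its instruction, "Perform a 12-lead ECG", stands in the pre-dose and baseline list, and the post-dose list has no ECG. The same instruction returns in section 7.1.7 for Day 8.

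The make-up rule is in Table 1, footnote 14: "The diamond reflects tests, examinations, assessments or other procedures that are to be completed the EoT visit if a participant is prematurely discontinued" and "the particular protocol-mandated activity was not performed at the Study Day 8 visit". In the EoT column that diamond is on weight, physical exam, saliva and the wearable device.

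Section 7.1.8 repeats the make-up in words: "Perform a brief physical exam and obtain weight (only if Study Day 8 visit was not completed" and "Obtain saliva sample for epigenetic analysis (only if Study Day 8 visit was not completed". Section 7.1.9 repeats the exam and weight at the 3-month visit under the same condition. None of these lists has an ECG.

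Among the primary endpoints, section 4.4.1 lists adverse events "related to clinically significant ECG/cardiac abnormalities". Section 9.4 pauses the study if one participant shows confirmed QT prolongation on a series of three ECGs. Its window runs from dosing through Day 30/EoT and expressly includes participants who have discontinued.

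On timing, section 4.1 encourages participants who discontinue after dosing to return "for the EoT visit as soon as possible and need not wait till Study Day 30".

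**The concern.** The make-up rule exists so that a participant who leaves before Day 8 still supplies what Day 8 would have supplied. As written, it recovers an exploratory saliva sample but not the one scheduled tracing that could show an ECG abnormality after dosing.

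Two parts of the plan depend on that tracing. One is the ECG component of the primary endpoint, since an abnormality without symptoms is found only if someone records an ECG. The other is the QT pause criterion, which claims to cover discontinued participants but has no scheduled measurement behind it for those who leave before Day 8.

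The people affected are not a random subset. Section 4.2 names adverse effects among the reasons for discontinuation. Section 7.1.1 lets the Investigator replace participants who stop by about Day 3, but not those who stop because of an adverse event. Those left without a post-dose ECG may therefore include participants of particular safety interest.

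**Working it through.** The plan gives no figure for this point, so there is none to reproduce. The check is a count of scheduled ECGs and a comparison of passages.

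**1. Scheduled post-dose ECGs by visit** (Tables 1 and 2, sections 7.1.4 to 7.1.9)

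| Visit | Post-dose ECGs |
|---|---|
| Day 1, after dosing | 0 |
| Day 2 | 0 |
| Day 4 (virtual) | 0 |
| Day 8 | 1 |
| Day 30 / EoT | 0 |
| 3-month follow-up | 0 |

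The total is 1 with Day 8 and 0 without it. With an ECG added to the EoT make-up list, a participant who misses Day 8 but attends EoT has 1. Table and visit text agree, so the gap does not come from a broken table.

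**2. Every Table 1 row marked at Day 8, and its EoT cell**

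- X at EoT: medical history, vital signs, clinical laboratory tests, GAD-7, PHQ-9, NIH-HEALS, BPI, C-SSRS, WCS, adverse events.
- Diamond at EoT: weight, physical exam, saliva.
- Neither: electrocardiogram.

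The ECG is the single exception, which looks more like an oversight than a choice.

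**3. The 7.1.8 sentence that could fill the gap**

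Section 7.1.8 says that, for discontinued participants, the Day 8 visit should be scheduled as soon as practical. Read literally, that brings in the Day 8 ECG. Set beside the other passages, it does not fit:

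- The preceding sentence in 7.1.8 says that a participant discontinued before Day 8 has the additional tests at the EoT visit.
- Footnote 14 places the make-up at EoT.
- Section 4.1 asks for the EoT visit promptly.
- Section 5.3 asks withdrawn participants to return for the EoT activities.
- The end of 7.1.8 makes EoT their last visit unless an adverse event is ongoing.

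The sentence may be a slip for the EoT visit. The document does not settle it.

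**4. Timing** (psilocin half-life about 108 minutes, section 2.3.2)

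- Day 8: 7 × 24 × 60 / 108 = 93 half-lives after dosing.
- EoT at Day 30 ± 5 days, that is 24 to 34 days after dosing: 24 × 1,440 / 108 = 320 to 34 × 1,440 / 108 = 453 half-lives.
- EoT for an early discontinuer: as soon as possible, so it may fall near or before Day 8.

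**5. How likely is it that someone is affected?**

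The protocol gives no rate of missing Day 8. Assume each of 24 treated participants misses it independently with probability d. The chance that at least one does is 1 − (1 − d)^24:

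- d = 5%: 1 − 0.95^24 = 71%
- d = 10%: 1 − 0.90^24 = 92%
- d = 20%: 1 − 0.80^24 = 99.5%

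The expected numbers are 24 × d = 1.2, 2.4 and 4.8 participants.

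**The case against.** **The protocol may already provide the ECG.** Taken literally, the 7.1.8 sentence gives early discontinuers a Day 8 visit with its ECG. This stands as a possible reading, so the point is in part a conflict to be resolved. The sentence does not help someone who misses Day 8 but stays in the trial; the make-up lines that apply to that person omit the ECG.

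**A late ECG says little about a single dose.** This stands for participants who remain in the trial and are seen at about Day 30. For early discontinuers it is weaker, because their EoT can come at or before the time the plan itself chose for everyone else.

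**Other safety follow-up exists.** Vital signs, laboratory tests and adverse events are all collected at EoT, and section 5.3 keeps participants withdrawn for adverse events under monitoring until resolution unless they refuse. This stands and narrows the gap to abnormalities that only a tracing would show. Return for EoT is also voluntary (5.3), so the fix will not recover everyone.

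**Stronger readings that the document does not support.** A reader might infer that these participants can never have an ECG after dosing. The protocol schedules none for them but does not rule out an unscheduled one. A reader might also infer that they will be counted as free of ECG abnormality, since section 12.1 analyses everyone dosed. Section 12.1 defines the analysed population and does not say that a missing ECG is scored as normal; handling of missing assessments can be left to the statistical analysis plan. Nor can the loss be expressed as a wider confidence bound on the event rate: the safety analysis is descriptive and plans no such bound.

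**Conclusion.** The point holds as a gap in the schedule. Under footnote 14 and the visit lists, a participant who discontinues before Day 8 has no scheduled post-dose ECG, although a primary endpoint component and a study pause criterion both rely on ECG findings. The size is 0 instead of 1 scheduled tracing for each such participant. How many there will be is unknown; if the chance of missing Day 8 is 5% to 10% (an assumption), the probability that at least one of 24 does is 71% to 92%.

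The gain from closing the gap is mainly for early discontinuers and is small for those first seen again at about Day 30. The conclusion assumes that the 7.1.8 sentence does not mean a separate Day 8 visit. If it does, discontinued participants are covered, and what remains is the contradiction with footnote 14, 4.1 and 5.3, plus the uncovered participant who misses Day 8 and stays in.

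A separate limitation remains: even full attendance gives no scheduled ECG after dosing on Day 1. The correction here does not address acute effects.

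**What to change.** - In Table 1, add the make-up diamond to the Electrocardiogram row in the EoT column.
- In section 7.1.8, add a 12-lead ECG line with the same condition as the exam and saliva lines, namely that the Day 8 visit was not completed.
- Reconcile the 7.1.8 sentence about scheduling the Day 8 visit with footnote 14, section 4.1 and section 5.3, so that it is clear which visit a discontinued participant attends and what is done there.
- When ECG findings are reported, state how many participants had a post-dose ECG.

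The cost is one table mark, one line, one clarified sentence, and one ECG, already planned for Day 8, for each of the few who missed it.
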